- H1.1.** CT will produce significant improvements on a composite measure of cognitive training performance on the POSIT Science BrainHQ tasks (Posit Composite Score) compared to the treatment control condition. This aim will be assessed at the end of Phase 1.
- H1.2.** tDCS combined with CT will produce significant improvements on a composite measure of attention, working memory, processing speed, and executive function (NIH Toolbox Fluid Cognition Composite Score, NIHTB FCCS) compared to the sham treatment control condition. FCCS will serve as the study primary outcome measure.
- H1.3.** Near and far transfer of CT and tDCS will occur, as assessed by the UM Functional Battery Composite Index and comprehensive neurocognitive assessment.

Aim 2. Determine whether CT combined with tDCS leads to greater functional and metabolic brain changes (fMRI, MRS). Effects will parallel Aim 1.

[figure not shown]
- H2.1.** Compared to TC, CT will decrease activation in working memory and attentional brain systems (dorsolateral prefrontal cortex, medial frontal cortex, inferior parietal lobe, supplementary motor association cortex), reflecting increased neural efficiency.
- H2.2.** Combined CT + tDCS will potentiate these effects.
- H2.3.** Cerebral metabolite alterations will occur secondary to CT and tDCS, with long-term increases in GABA and N-acetyl aspartate (NAA) concentrations, and decreased choline (Cho) and myoinositol (MI) concentrations in the frontal cortex and posterior parietal cortex. CT and tDCS will modulate MRS GABA in frontal areas.

Exploratory Aim. Examine which baseline factors (e.g., clinical, demographic, neuroimaging, cognitive) best predict individual differences in neurocognitive and functional outcome.

- HE.1.** White matter abnormalities on FLAIR MRI will predict poorer outcome.
- HE.2.** Metabolic-vascular risk factors/disorders (e.g., diabetes) will be predictive of reduced outcome.
- HE.3.** Alzheimer’s disease risk factors (APOE4 and familial history) will predict poorer outcome.

6. Research Plan:

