Aim 2. Determine critical tDCS current properties and specific brain regions associated with responder vs. non-responder to tDCS and CT intervention using machine learning.

H2.1. Current intensity and direction will significantly predict response vs. non-response to tDCS and CT intervention on the NIH Toolbox Fluid Cognition Composite Score (ACT primary outcome).

H2.2. Current intensity and direction within bilateral rostral middle frontal, right superior frontal and frontal pole, and left pars orbitalis regions will most strongly predict response vs. non-response to tDCS and CT intervention.

H2.3. Current intensity and direction will outperform clinical/demographic characteristics alone (e.g., age, sex, comorbidities, mental health, Alzheimer's disease risk, cognition, etc.) in predicting tDCS response.

Exploratory Aim. Evaluate computational methods for achieving precision delivery of dosing characteristics in tDCS.

HE.1. Adjusting tDCS current intensity input into computational models will achieve precision delivery of targeted dosing characteristics.

HE.2. Adjusting electrode locations input into computational models will achieve precision delivery of targeted dosing characteristics.

No new data will be collected from participants to achieve these aims. Only existing data collected with consent from participants in the course of the primary ACT study will be used. These data will be analyzed using advanced analytic methods (computational modeling and machine learning) to achieve all three aims specified in section 6.18.

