Aim 1. Dependent measures. The primary dependent measure in Aim 1 is current density computed in individual head models from existing MRIs. Current components will be further quantified as current intensity and direction. **Rationale.** Computed current density will provide an estimate of tDCS current dose within brain regions unique to each person's neuroanatomy. **Outcome analyses.** **H1.1.** The regression analysis between current density (dependent variable) and anatomical measures (independent variable) e.g., brain volume ratio, sulcus depth, bone thickness will test the hypothesis that unique current density distribution in each person is significantly affected by individual characteristics in neuroanatomy. **H1.2.** Current characteristics generated from models will be compared between inclusion and exclusion of white matter lesions. A false discovery rate (FDR)-corrected voxel-wise within participants analysis will test the hypothesis that inclusion of white matter lesions in computational models significantly alters current characteristic predictions.

Aim 2. Dependent measures. The primary dependent measure in Aim 2 is balanced accuracy. This measure provides an overall index of the performance to differentiate responders from non-responders. **Rationale.** By using this measure, we provide a single performance indicator upon which the **heterogeneity of response** in tDCS augmented CT can be revealed. Much of our preliminary data is based on analyses using this measure. **Outcome analyses.** All analyses will be conducted with the intent to optimize prediction of tDCS outcome. McNemar test at one-tailed 0.05 significance level will be conducted to determine whether current intensity and direction will outperform clinical and demographic characteristics alone in predicting tDCS response.

Exploratory Aim. Dependent measures. The primary dependent measure in the Exploratory Aim is log-likelihood distance measure. Adjustments of electric current intensity and electrodes placement in computational models will be used to minimize the log-likelihood distance measure to the Gaussian Mixture Model of the responders' current distribution.

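### Section 6.18, Aim 2 analyses the FCCS only as responder versus non-responder, with no stated cut, and so discards information the trial already collects

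*Combined protocol and SAP*

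**What the plan says.** Under Specific Aims, H1.2 names the NIH Toolbox Fluid Cognition Composite Score and states that "FCCS will serve as the study primary outcome measure".

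Section 6.18 adds a later analysis of the same data. Its Aim 2 uses the score as a two-class label throughout:

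- H2.1: the modelled current's intensity and direction are expected to "predict response vs. non-response to tDCS and CT intervention on the NIH Toolbox Fluid Cognition Composite Score".
- Aim 2, dependent measures: "The primary dependent measure in Aim 2 is balanced accuracy". Of this it says: "This measure provides an overall index of the performance to differentiate responders from non-responders".
- H2.3, current characteristics against clinical and demographic characteristics alone: "McNemar test at one-tailed 0.05 significance level will be conducted".
- Exploratory Aim: intensity and electrode placement are varied inside the computational models to "minimize the log-likelihood distance measure to the Gaussian Mixture Model of the responders' current distribution".

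Section 6.18 does not say what makes someone a responder. It gives no threshold, visit, expected responder share, Aim 2 sample size or FCCS reliability. Regression is specified only in Aim 1, where current density is the outcome. The opening of the section refers in general terms to trial outcomes, but the Aim 2 analysis text is classification only.

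**The concern.** Once a score is split, a person just above the cut counts the same as one with a large gain, and a person just below counts as having none. A real relation between modelled current and FCCS becomes harder to detect. The stated purpose of Section 6.18 is to explain differences in response, so a null result caused by avoidable loss of information would defeat it.

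The label also rests on one person's observed result, which carries measurement error. People near the cut can fall in the wrong class, and the Exploratory Aim builds its target distribution from whoever is labelled a responder. With no rule stated, the cut could also be chosen after the allocation is known. No clinical threshold is given that would justify accepting these costs.

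**Working it through.** **Plan's own figure.** There is none to reproduce: Section 6.18 states no power, cut or information figure. The only design arithmetic, 80 + 280 = 360 (Section 6.1), is consistent.

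**1. Number of people.** Phase 1 has 80 participants in four arms at 1:1:1:1, and Phase 2 has 280 in two arms at 1:1 (Sections 6.1 and 6.2). CT + active tDCS is 80/4 + 280/2 = 20 + 140 = 160 randomised. If CT and TC are collapsed, active tDCS is 20 + 20 + 140 = 180. Dropout is not stated; an assumed 10–20% would leave 144–128 of the 160. Aim 2 gives no n of its own, so 160 is an inference.

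**2. Information kept by one cut.** With normal residuals and a small linear effect, a cut at responder share p keeps φ(z_p)² / [p(1 − p)] of the information in the continuous score. At p = 0.5 this is 0.3989² / 0.25 = 2/π = 0.637.

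| Split | Kept | Lost | Effective n of 160 | of 180 |
|---|---|---|---|---|
| 50/50 | 63.7% | 36.3% | 101.9 | 114.6 |
| 40/60 | 62.2% | 37.8% | 99.5 | 111.9 |
| 30/70 | 57.6% | 42.4% | 92.1 | 103.6 |
| 25/75 | 53.9% | 46.1% | 86.2 | 96.9 |
| 20/80 | 49.0% | 51.0% | 78.4 | 88.2 |

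The median split is the best single cut. Matching 160 people with the continuous score would take 160/0.637 ≈ 251 with a median split.

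**3. How far that depends on its assumptions.**

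- Against least squares, a median split keeps 4f(0)²σ². For logistic residuals this is 4 × (1/4)² × π²/3 = 0.82, a loss of 18%. For t(5) residuals it is 0.96, a loss of 4%.
- Against an estimator suited to those tails, the losses are 25% (logistic) and 23% (t(5)).
- Comparing the top and bottom 27% and dropping the middle keeps 2φ²/p = 81%, a loss of 19%.

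**4. Illustrative power.** This uses one predictor, n = 160, a two-sided 5% test and Fisher's z: power = Φ(atanh(r)·√157 − 1.96). The correlation of 0.22 is an assumption, chosen because it gives 80% power with the continuous score. A cut multiplies r by the square root of the share kept.

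- Continuous: atanh(0.22) × 12.53 − 1.96 = 0.84, power 80%.
- Median split: r = 0.22 × 0.798 = 0.176, power 60%.
- 30/70: r = 0.22 × 0.759 = 0.167, power 56%.
- 25/75: r = 0.22 × 0.734 = 0.161, power 53%.

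A 20,000-run simulation gave 80.5% (continuous), 60.8% (median split) and 53.0% (25/75).

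**5. Label error.** The documents give no reliability, so this is shown only as a range. If the FCCS change has reliability R, the share wrongly labelled at a median split is arccos(√R)/π, and balanced accuracy against the observed labels cannot exceed one minus that, even with perfect knowledge of true response. The matching ceiling on R-squared for the continuous change is R itself.

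| Assumed R | Wrong labels | Balanced-accuracy ceiling | R-squared ceiling |
|---|---|---|---|
| 0.4 | 28% | 0.72 | 0.40 |
| 0.5 | 25% | 0.75 | 0.50 |
| 0.7 | 18.5% | 0.81 | 0.70 |
| 0.9 | 10% | 0.90 | 0.90 |

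Both forms of the outcome have a ceiling. The difference is that a cut converts the error into class membership, which the responder-only mixture model then uses.

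**The case against.** The best case for the plan is that classification is what Aim 2 sets out to do. The section gives a reason: balanced accuracy is one overall indicator, and much of the preliminary work used it. Section 6.18 is also a secondary analysis of existing data, with no effect on participation. The comparability argument stands, and it is a reason to keep balanced accuracy as a secondary measure. Wanting a single indicator does not favour a split, because out-of-sample R-squared is also one number.

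A reader might infer more than the documents support:

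- **That at least 36% of the information is certain to be lost.** That holds for one cut with near-normal residuals. The rule is not stated, so no figure can be fixed for this plan.
- **That the planned tests lose about 20 points of power.** The calculation is for a one-predictor correlation at an assumed size. Aim 2 uses machine learning, balanced accuracy and a one-tailed McNemar test.
- **That the continuous score removes the noise behind wrong labels.** It does not, since error in FCCS change also limits R-squared. Baseline adjustment reduces that error without removing it.
- **That the mixture-model target must give way to a fitted dose-response surface.** Such a surface over intensity and direction is not shown to be estimable at this sample size, and the choice is open to debate.

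**Conclusion.** The point holds as a cheap improvement. Section 6.18 uses the primary outcome score only as an undefined two-class label and specifies no continuous FCCS analysis alongside it, so it gives up information already collected. With a single cut and near-normal residuals the loss is at least about 36%, and about 42% at 30/70; it is smaller with heavy tails or an extreme-groups rule. The fall in power from about 80% to about 60% is an illustration. It assumes a correlation of 0.22 and 160 randomised (180 if groups are collapsed, fewer after dropout).

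Class errors passed on to the responder-only target are a real added cost of the cut, but their size is unknown without a reliability figure. The missing threshold and visit are certain from the text. The primary comparison (H1.2) and participants' treatment are not affected.

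**What to change.** Before unblinding, amend Section 6.18 as follows.

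1. Make follow-up FCCS, adjusted for baseline FCCS and kept continuous, the primary Aim 2 target, at a named visit. Judge prediction from current intensity and direction by out-of-sample R-squared or squared error.
2. Test H2.3 by the paired difference in out-of-sample squared error between the model with current characteristics and the model with clinical and demographic characteristics alone.
3. Keep balanced accuracy and the McNemar test as secondary, with the responder threshold and visit written down in advance.
4. Report the exploratory mixture-model work as conditional on those labels.

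The cost is a rewording and a regression learner where a classifier was planned. No new data are needed. Section 6.18 releases the allocation only after all follow-up visits, so the change can be made before Aim 2 begins. The downside is less direct comparability with the preliminary balanced-accuracy results, which the secondary analysis largely preserves.

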We will leverage existing multimodal neuroimaging and behavioral outcomes data from the ACT trial to 1) **elucidate mechanism of action** underlying response to tDCS treatment with CT, 2) **address heterogeneity of response** in tDCS augmented CT by determining how individual variation in the dose of electrical current delivered to the brain interacts with individual brain anatomical and lesion characteristics; and 3) **refine the intervention strategy** of tDCS paired with CT by evaluating computational methods for estimating precision delivery of targeted dosing characteristics to facilitate tDCS augmented outcomes. We will employ state of the art MRI-derived computational modeling and machine learning (ML) applied to existing data to 1) create precision individualized computational models of electrical current in the brain from tDCS for all 360 participants in ACT (based in T1 weighted images), 2) determine the characteristics of electrical current calculated from electric current models associated with trial outcomes, and 3) evaluate a computational method for calculating possible precision dosing of tDCS parameters for optimizing trial outcomes in older adults.

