To date, all prior trials of tDCS have applied a fixed dosing strategy (e.g., 2mA for 20 min with electrodes at F3/F4 [10-20 measurement system]) in attempts to enhance CT – including ACT. However, prior research demonstrates that individual variability in head and brain anatomy (e.g., degree of atrophy, skull thickness, etc.) significantly alters the spread and intensity of direct electrical current delivered to the brain person to person. The impact of individual variation in electrical current delivered to the brain for clinical outcomes has rarely been examined, and methods aimed at increasing stimulation effectiveness and optimizing readiness to learn are only now beginning to be explored. We will use advanced MRI-derived computational modeling of electrical current from existing MRIs to provide a means for accurately estimating individual differences in tDCS current delivery to the brain in the largest existing sample of participants undergoing tDCS (i.e., ACT) with multimodal neuroimaging data. When combined with state-of-the-art machine learning approaches and behavioral outcome data (only unblinded once ACT has completed all follow-up visits), precision models of tDCS current will be derived to identify critical stimulation dosing characteristics (e.g., current intensity, direction/path of current) in specific brain regions associated with response vs. non-response to tDCS and CT intervention. These data will not only provide much needed information for determining how individual participant characteristics impact tDCS efficacy, but will also serve as a foundation for future precision medicine applications of tDCS and CT to remediate cognitive decline in older adults and potentially prevent or alter the trajectory towards Alzheimer's disease.

Aim 1. Determine inter-individual variability in tDCS current distribution using MRI-derived finite element modeling.

H1.1. Variability in neuroanatomy (e.g. increased atrophy, sulcus depth, skull thickness, etc.) will significantly decrease current intensity and alter the pathway/direction of electrical current flow induced by tDCS in the brain.

H1.2. White matter lesions, as measured by white matter hyper-intensities on FLAIR imaging, will significantly decrease current intensity and significantly alter the direction of electrical current flow induced by tDCS.

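### Ancillary H1.2 (section 6.18) is judged by whether adding lesions to a model significantly alters its output, with no required size or direction, although the hypothesis predicts a decrease in current intensity

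*Combined protocol and SAP*

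**What the plan says.** Section 6.18 re-uses trial data to model current flow in each participant's head, "for all 360 participants in ACT (based in T1 weighted images"). Under Aim 1, H1.2 states that white matter lesions seen on FLAIR "will significantly decrease current intensity and significantly alter the direction of electrical current flow induced by tDCS".

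The outcome is a model output: "The primary dependent measure in Aim 1 is current density computed in individual head models from existing MRIs". For H1.2, "Current characteristics generated from models will be compared between inclusion and exclusion of white matter lesions". The test is "A false discovery rate (FDR)-corrected voxel-wise within participants analysis", and the statement it is to support is that "inclusion of white matter lesions in computational models significantly alters current characteristic predictions".

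The section also says "No new data will be collected from participants to achieve these aims", so it plans no measured current against which the models could be checked.

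For H1.2, section 6.18 does not state the FDR level, whether the test is one- or two-sided, the conductivity given to lesion tissue or any range for it, the voxels or regions that must differ, or the smallest change that would count as relevant.

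**The concern.** Three features combine.

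- **Source of the difference.** Each pair is one head solved twice, and only the representation of lesion tissue changes. Rejecting a null of no difference says little about whether lesions matter for the current delivered.
- **Size.** With several hundred pairs, a small but consistent shift can be significant. No criterion separates a negligible change from one that matters.
- **Direction.** H1.2 predicts a decrease in intensity. The analysis paragraph tests only for alteration, so an increase would satisfy the test and contradict the hypothesis.

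At stake is what Aim 1 can conclude. Section 6.18 treats computed current as the estimate of dose in each brain region, and Aim 2 and the Exploratory Aim build on it. The useful question is whether lesions change that estimate enough to need modelling, and a map of significant voxels does not answer it.

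**Working it through.** The plan gives no sample size, power or effect size for H1.2, so there is no stated figure to reproduce. Three checks follow.

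**1. Hypothesis against test (both in section 6.18)**

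| Element | Specific aims, H1.2 | Outcome analyses, H1.2 |
|---|---|---|
| Subject | Current induced by tDCS | Model predictions |
| Intensity | Decrease | Altered, no sign |
| Direction of flow | Altered | Altered |
| Size needed | Not stated | Not stated |

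The two agree on direction of flow but not on intensity.

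**2. Size of shift that a paired test detects**

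Inputs: n = 360 pairs (section 6.18); two-sided 0.05, one comparison (assumption). Effects are in units of the between-person SD of the paired differences.

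- Smallest observed mean that reaches p < 0.05: t(0.975; 359)/√360 = 0.104 SD.
- Mean shift with 80% power: (1.960 + 0.842)/√360 = 2.802/18.97 = 0.148 SD.
- Power is 0.81 at 0.15 SD, 0.97 at 0.20 SD and about 1.00 at 0.30 SD.

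The documents do not give the SD of the percentage change, so a range is shown:

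| Assumed SD of paired change | Mean change with 80% power (0.148 × SD) |
|---|---|
| 1% | 0.15% |
| 3% | 0.44% |
| 10% | 1.5% |
| 30% | 4.4% |

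The planned test is FDR-corrected, so its cut-off per voxel is stricter. How much stricter depends on how many voxels differ, which is unknown. For a 0.148 SD shift, power at illustrative cut-offs per voxel is 80% at 0.05, 24% at 0.0005, 10% at 0.00005 and 2% at 0.000001. Larger shifts stay detectable: at 0.30 SD, power is 96% at a cut-off of 0.0001.

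**3. Does a count of significant voxels track the size of the change?**

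An illustrative two-dimensional conduction model was solved twice per simulated head, the two runs differing only in the conductivity of lesion tissue. Assumptions, none from the documents: 28 × 28 = 784 voxels, 0 to 4 small lesions per head, 360 heads, a two-sided paired t-test per voxel, Benjamini-Hochberg at q = 0.05.

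| Lesion conductivity ÷ normal | FDR-significant voxels | Mean change in current density within lesions |
|---|---|---|
| 0.50 | 675/784 | −38% |
| 0.95 | 674/784 | −3.4% |
| 1.00 | None; every difference is exactly 0 | 0 |
| 1.05 | 674/784 | +3.3% |
| 2.00 | 667/784 | +57% |

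In this model the count hardly moves between a 5% and a 50% reduction in conductivity, while the change in lesion current differs about elevenfold (38/3.4). Its sign follows the value assigned to lesion tissue. This shows the mechanism only; it does not predict the trial's results.

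**The case against.** A reader might infer that the test cannot fail, or that its p-value reflects nothing but the number of heads. The documents do not support that.

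- Lesions are taken from each participant's FLAIR scan, so their load and location are real between-person data. A paired test depends on the mean difference relative to its between-person SD, and so on how consistent the change is across people.
- A difference within one head does not force a non-zero mean at a given voxel. Where lesions are rare or signs cancel, the mean can be close to zero. In the illustration, 784 − 675 = 109 voxels (14%) were not significant even at the strongest reduction in conductivity.
- The predicted decrease in intensity could turn out false.
- The plan does not say that one significant voxel would be enough.
- The 0.148 SD figure is for a single uncorrected test, and its meaning in per cent depends on an SD that nobody has stated. At an SD of 30%, the detectable change is 4.4%, which need not be trivial.

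All of this stands, and it limits the point. It does not supply the missing size criterion or put the predicted sign into the test. Nor does it remove the dependence on the lesion conductivity chosen. A further fair objection is that a percentage change computed at one conductivity is just as much set by the modeller as a p-value is; for that reason the fix includes a range of conductivities.

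**Conclusion.** The concern holds in a limited form. As written, a significant result for H1.2 would show that including lesions shifts the model output consistently at some voxels. It would not show that the shift is large enough to matter, and for intensity it would not show that the shift is in the predicted direction.

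The mismatch between decrease and alteration, and the absence of a size or region criterion, can be read directly from section 6.18 and need no assumption. How small a change could be declared significant does rest on assumptions: 0.148 SD for one uncorrected comparison with all 360 pairs, or about 0.15% to 4.4% for SDs of 1% to 30%, and more than this after FDR correction.

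A reader might go further and conclude that the head models, Aim 2 or the trial result are undermined. Nothing here supports that. Section 6.18 is a secondary use of existing data, and H1.2 does not bear on the primary outcome, the NIH Toolbox Fluid Cognition Composite Score. This is a minor point and a cheap improvement.

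**What to change.** In the Outcome analyses paragraph for H1.2 in section 6.18:

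1. Make the outcome the signed paired percentage change in current intensity (with lesions minus without, relative to without) and the angular change in direction, each with a 95% CI.
2. Report both in prespecified regions. The frontal regions already listed in H2.2 are one option; they were chosen for predicting response, so the sponsor should confirm that they suit H1.2.
3. Show the change against FLAIR lesion volume.
4. Repeat the comparison over a stated range of lesion conductivities, and say whether the conclusion holds across it.
5. Interpret the results against a relevance size fixed before the with/without comparison is examined. This is essential for direction, because an unsigned angle is never below zero and a comparison with zero is uninformative. Model construction was estimated to start in January 2021 and take about 24 months, so the models may already be in progress; the relevance size can still be set before the comparison is opened.
6. Count only a decrease in intensity as support for the intensity part of H1.2, and align the hypothesis with the analysis text.
7. Keep the FDR-corrected map as a descriptive figure, with its FDR level stated.

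The cost is some SAP wording, one summary table and some model re-runs for the conductivity range. No new participant data are needed. The harder part is that the sponsor must commit to a relevance size.
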